2.4. Phase 2a, Expansion Phase

Once the RP2D has been determined in the Dose-Determination Phase, the following cohorts will be enrolled and treated with exicorilant + enzalutamide according to the RP2D regimen. The DRC may elect to expand more than 1 dose level, if needed, to better define the RP2D.

- **Abiraterone (Abi)-Resistant Cohort:** Patients who have progressed during treatment with abiraterone and have received no other AR-blocking therapies (N≈20)
 - **Food-Effect Subcohort:** The effect of food on the PK of exicorilant will be evaluated in 10 patients enrolled to the Abi-Resistant Cohort. These 10 patients will have a 7-day Lead-In Period as follows:
Day -7: Single oral dose of exicorilant administered under fasting conditions.
Day 1: Single oral dose of exicorilant administered 30 minutes after a standard breakfast. These patients will initiate enzalutamide on Cycle 1 Day 2 to avoid confounding the assessment of the effect of food on exicorilant PK.
Patients in the Abi-Resistant Cohort who do not participate in the food-effect study will not have a Lead-In Period.
- **AR Antagonist (ARant)-Resistant Cohort:** Patients who have progressed during treatment with enzalutamide or second-generation AR-blocking therapies (N≈20). Note: Patients in the ARant-Resistant Cohort will not have a Lead-In Period.

3. Study Objectives

3.1. Primary Objective

The primary objective of this study is to determine the MTD and/or biologically active doses of exicorilant in combination with enzalutamide to identify the recommended dose for Phase 2 studies (RP2D).

3.2. Secondary Objectives

The secondary objectives of this study are to:

- Evaluate the safety and tolerability of exicorilant in combination with enzalutamide.
- Characterize the preliminary efficacy of exicorilant in combination with enzalutamide by determining the objective response rate (ORR), proportion of patients with a reduction in prostate-specific antigen (PSA) level by >50%, time to a symptomatic skeletal event (SSE), radiographic progression-free survival (rPFS), including the

- proportion of patients who are progression-free at 4, 6, and 12 months, duration of response (DOR), and overall survival (OS).
- Assess time to biochemical (PSA progression) bone disease progression, and clinical progression, including the proportion of patients who are progression-free at 4, 6, and 12 months.
 - Determine the PK profile of exicorilant and enzalutamide, when co-administered.
 - Determine the effect of food on the PK of exicorilant.

3.3. Exploratory Objectives

Exploratory objectives of this study are to:

- Evaluate the effects of exicorilant in combination with enzalutamide on the hypothalamic pituitary-adrenal (HPA) axis, including assessments of:
 - Urinary free cortisol (UFC)
 - Serum cortisol
 - Plasma adrenocorticotrophic hormone (ACTH)
- Explore the antitumor activity of the combination of exicorilant and enzalutamide by line of therapy and in specific sub-sets of disease, including:
 - GR+ vs. GR-, by tumor immunohistochemistry (IHC) and/or circulating tumor cells (CTCs)
 - Androgen-receptor splice variant 7 messenger RNA (ARV7) status
 - Systemic antagonism of cortisol activity as assessed by whole blood transcriptional profiling
- Assess change in PSA.
- Conduct correlative analysis of exposure-response for measures of efficacy and changes in GC-modulated pathways, adrenocorticotrophic hormone (ACTH)/cortisol, or other PD markers.
- Assess the effect of pharmacogenomics polymorphisms of the cytochrome P450 pathway on PK and PD parameters (Dose-Determination Phase Segment 1 only).
- Explore the effects of exicorilant and enzalutamide on patient-reported outcomes (PRO) and quality of life (QoL).

4. Study Endpoints

The study has primary safety and secondary efficacy, safety and PK endpoints. Exploratory endpoints include efficacy, PD, PRO and QoL endpoints.

4.1. Primary Endpoint

This study includes a DLT endpoint to meet the primary objective of determining MTD and/or biologically active doses of exicorilant in combination with enzalutamide and to identify the RP2D.

DLTs will be recorded during the DLT-evaluation period (first dose of exicorilant through completion of Cycle 1 for Segment 1, or first dose of exicorilant through completion of Cycle 3 for Segment 2). The study protocol Section 5.5 defines a DLT as any of the following toxicities that the investigator considers possibly or probably related to study drug that occur during the DLT evaluation period:

- Hematologic DLT:
 - Grade 4 neutropenia for > 7 days.
 - Febrile Grade 3 or 4 neutropenia (absolute neutrophil count [ANC] <1000/mm³ and a single temperature of >38.3°C [101°F] or a sustained temperature of ≥38°C [100.4°F] for more than 1 hour).
 - Grade 3 thrombocytopenia with bleeding.
 - Grade 4 thrombocytopenia.
- Non-Hematologic DLT:
 - Grade 3 or greater toxicity according to National Cancer Institute Common Terminology for Adverse Events (NCI-CTCAE) v4.03 that represents at least a 2-grade increase from baseline and is not attributable to disease or disease-related processes, with the following exceptions:
 - Grade 3 fever.
 - Grade 3 fatigue, nausea, vomiting, constipation, or diarrhea that resolves to Grade 2 or less within 48 hours after standard therapy.
 - Grade 3 changes in electrolytes not associated with signs or symptoms and that resolve within 3 days off therapy. An increase in gamma-glutamyl transferase (GGT) or alkaline phosphatase alone will not be considered a DLT.
 - Transient Grade 3 increase in creatinine or dehydration lasting ≤24 hours corrected with IV fluids if needed.
 - ALT >3x ULN with concomitant total bilirubin of >2x ULN.
- Grade 2 toxicity that represents at least a 2-grade increase from baseline, which requires dose modification or delay of >1 week.
- Failure to receive >25% of the doses during the DLT period due to toxicity.
- Dose delay due to AE of greater than 2 weeks.

Occurrences of DLTs will be collected by medical operation personnel and reviewed with investigators. These data will be used for the analysis of DLTs.

Per protocol Section 5.6, the MTD for exicorilant in combination with enzalutamide is the highest dose at which the DLT rate is <33% within the DLT-evaluation period. The DRC may determine a biologically active dose of exicorilant prior to reaching MTD based upon reliable evidence of GR antagonism and assessment of exposure-response for PD, tolerability, and efficacy. The RP2D of exicorilant in combination with enzalutamide will take into account overall tolerability, PD markers of target engagement, and PK. The RP2D will always be ≤ MTD.

4.2. Secondary Endpoints

4.2.1. Secondary Safety Endpoints

The safety and tolerability will be assessed by evaluating the following endpoints:

- Incidence of adverse events (AEs), serious AEs (SAEs), treatment-related AEs, AEs by severity, deaths
- Discontinuations of treatment and study withdrawal due to AEs
- Dose interruptions and reductions due to AEs
- Change from Baseline in clinical laboratory tests
- Change from Baseline in vital signs (including blood pressure, heart rate)
- Shift from Baseline in 12-Lead Electrocardiogram (ECG)
- Change from Baseline in Eastern Cooperative Oncology Group (ECOG) performance status

4.2.2. Secondary Efficacy Endpoints

Efficacy will be assessed by evaluating the following endpoints:

- ORR: proportion of patients with an objective tumor response (either partial response [PR] or complete response [CR]) per investigator using RECIST v.1.1 in patients with measurable disease, including best radiographic response for soft tissue.
- A reduction in PSA level from baseline by 50% or more.
- Time to SSE defined as symptomatic fracture, radiation or surgery to bone, or spinal cord compression.
- rPFS: time from first dose of study treatment (exicorilant and/or enzalutamide) to the date when the first site of disease is found to progress on computed tomography (CT), magnetic resonance imaging (MRI), or radionuclide bone scan per the Prostate Cancer Working Group 3 (PCWG3) criteria, or death, whichever occurs first. Progression will be assessed by the investigator using RECIST v.1.1. The portion of patients who are progression-free at 4,6 and 12 months will also be summarized.
- DOR: time from the first occurrence of a documented objective tumor response (CR or PR) to the time of radiographic progression (per investigator using RECIST v.1.1) or death from any cause on study, whichever occurs first.
- Time to PSA progression, clinical progression (per investigator), and bone-disease progression.
- Overall survival: time from the first dose of exicorilant and/or enzalutamide to the date of death from any cause.

4.2.3. Secondary Pharmacokinetic Endpoints

PK will be assessed by evaluating the following:

- Standard PK parameters of exicorilant and enzalutamide will be estimated using non-compartmental methods to analyze the plasma concentration data for exicorilant and enzalutamide
- Determine the effect of food on the PK of exicorilant

4.3. Exploratory Endpoints

4.3.1. Exploratory Efficacy Endpoints

- Maximum reduction in PSA (% change) from baseline
- Best PSA response (i.e., the most post-baseline reduction in PSA (% change) among all the changes from every post-baseline PSA value to its prior largest PSA value)).

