9.5.5 Analyses of Anticancer Activity

The following endpoints will be summarized to meet the study secondary objective of characterizing preliminary efficacy:

- ORR, defined as the proportion of patients with an objective tumor response (either partial response [PR] or complete response [CR] per Investigator using Response Evaluation Criteria in Solid Tumors version 1.1[RECIST v1.1]) in patients with measurable disease, including best radiographic response for soft tissue
- A reduction in PSA level by $\geq 50\%$
- Distribution of the best PSA response
- Time to SSE defined as symptomatic fracture, radiation or surgery to bone, or spinal cord compression

- rPFS defined as the time from the first dose of study treatment (CORT125281 and/or enzalutamide) to the date when the first site of disease is found to progress on CT, MRI, or radionucleotide bone scan per PCWG3, or death whichever occurs first. Progression will be assessed by the Investigator using RECIST v1.1. The proportion of patients who are progression-free at 4, 6, and 12 months will also be summarized.
- DOR, defined as the time from the first occurrence of a documented objective tumor response to the time of radiographic progression (per Investigator using RECIST v1.1) or death from any cause on study, whichever occurs first
- Time to PSA progression, clinical progression (per Investigator), and bone disease progression
- Overall survival, defined as the time from the first dose of study treatment (CORT125281 and/or enzalutamide) to the date of death from any cause

Data summaries will include number, percent and waterfall displays as appropriate. Time-to-event endpoints will be characterized using Kaplan-Meier method.

For the analyses of rPFS and DOR, data for the patients who have not experienced disease progression or death will be censored at the time of the last tumor assessment date.

Data for the analysis of overall survival will be censored at the time of the end of follow-up period. Dose adjustments/changes in enzalutamide will be summarized by CORT125281 dose and overall.

The change in markers of disease status, such as PSA and CTCs, will be compared between the Lead-In Period and Cycle 1, when possible.

These analyses will be performed in the Safety Population and Response-Evaluable Population.

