7.2. Definitions

Study day: Study day will be calculated in reference to the date of the first dose of exicorilant. For assessments conducted on or after the date of the first dose of exicorilant, study day will be calculated as (assessment date - date of first dose of study drug + 1). For assessments conducted before the date of the first dose of exicorilant, study day is calculated as (assessment date - date of first dose of study drug). There is no study day 0.

Treatment-emergent period: The treatment-emergent period is defined as the period of time from the date and time of the first dose of exicorilant through 30 days after the last dose of

study drug (exicorilant or enzalutamide whichever is later). The treatment-emergent period will be used in the summaries of treatment-emergent adverse events (TEAEs).

Baseline and postbaseline value: Unless otherwise specified, a baseline value will be defined as the most recent value on or before the first dose of exicorilant including PRO, QoL and baseline characteristics. In addition, pretreatment Cycle 1 Day 1 values could serve as baseline. A postbaseline value is defined as an assessment obtained after the first dose of exicorilant.

Baseline and postbaseline value for safety analyses: Unless otherwise specified, a baseline value for safety analyses is defined as the last value on or before the date/time of first dose of exicorilant for laboratory tests, vital sign assessments, and ECG data. A postbaseline value for safety analyses is defined as a measurement taken after the date/time of first dose of exicorilant. If multiple toxicity grades are present for the same date, the worst toxicity grade will be used in the summaries of toxicity grade by laboratory tests. For triplicate measurements of ECG, worst results will be used in the summaries presented by visit. For all other safety parameters, if multiple measurements are present for the same date, latest available value will be considered for summaries.

Last dose date: Date of last dose of exicorilant or enzalutamide (whichever is last) from the end of treatment – exicorilant and enzalutamide eCRFs.

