9.1. Secondary Efficacy Endpoints

Objective Response Rate (ORR): Patient listings of tumor response outcomes (CR, PR, non-CR/non-progressive disease, stable disease, progressive disease, unevaluable, or not assessed) at study visits, as well as best overall response per RECIST v1.1, will be presented by treatment regimen dose group and overall for the ITT population. By-group summary tables will include distribution of response outcomes, best overall response derived over all visits, and point estimates with Clopper-Pearson² 95% CIs for ORR, defined as the proportion of patients with an objective tumor response (either PR or CR) in patients with measurable disease, including best radiographic response for soft tissue.

For supportive purposes, best overall response and point estimates with Clopper-Pearson 95% CIs for ORR will also be summarized using confirmed response.

PSA Levels: PSA levels recorded at each visit will be listed. Proportions of patients in the Safety population who experience a 50% or greater reduction in PSA levels at any visit since baseline will be reported with Clopper-Pearson 95% CIs by treatment group and overall. Mean reduction levels will be characterized via summary statistics. Median time from date of first dose of exicorilant to PSA progression (first occurrence of 50% or greater increase in PSA levels), along with 95% CIs will be estimated via Kaplan-Meier method, and also plotted graphically by treatment group. Patients who are alive and progression-free will be censored at the date of their-last PSA evaluation.

In dose escalation and expansion phases separately, best PSA response will be illustrated graphically via waterfall plots. For each patient, the maximum percent change in PSA levels since baseline will be depicted on the response axis, with vertical bars below the baseline representing decline in the blood-based marker.

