9.2. Exploratory Efficacy Endpoints

Change from baseline in PSA score: Summary statistics will be provided for PSA score at screening, baseline and at each of the post-baseline time points during the observation period. The changes of PSA score from baseline will be summarized by post-baseline visits. Patient data will be listed. Waterfall plots will be generated for maximum reduction in PSA (%) from baseline, and for best reduction in PSA (%) from any timepoint.

Patient Reported Outcomes (PRO) and Quality of Life (QoL) Assessments: PRO and QoL assessments will be listed and summarized using data from the Safety population.

The FACT-P questionnaire and additional questions to capture patient-reported pain will be used on study.

FACT-P: Patient responses to the 39 items of the instrument will be scored to obtain an overall and four subscale scores with lower scores indicating greater symptom burden. Possible ranges for the calculated scores would be:

- Overall (FACT-P): 0 – 156
- Physical Well-Being (PWB): 0 – 28
- Social/Family Well-Being (SWB): 0 – 28
- Emotional Well-Being (EWB): 0 – 24
- Functional Well-Being (FWB): 0 – 28
- Prostate Cancer Subscale (PCS): 0 – 48

Some items are reverse scored. Reversals will be performed as indicated by FACT-P Scoring Guidelines (Version 4) and individual items will be summed to obtain a score. If there are unanswered items, the total score will be multiplied by the number of items in the subscale and then divided by the number of items answered. This produces the subscale score. A higher score indicates better quality of life (QoL).

Health-related quality of life will be assessed in the Safety population and analysis subgroups (enzalutamide or abiraterone naïve, prior treatment with abiraterone, enzalutamide resistant, ARV7 positive and ARV7 negative, and GR positive and GR negative) using the FACT-P questionnaire at the time points shown in the SoA. Patients who discontinue exicorilant + enzalutamide due to reasons other than disease progression will continue to be assessed until unequivocal progressive disease is documented.

Patient listing for all subscales of FACT-P will be presented by visit and treatment group.

Specific endpoints to characterize the quality of life in patients will include:

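### The SAP gives best PSA response two reference values, and under the prior-peak one a PSA that never falls below baseline can be shown as a reduction

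*SAP*

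**What the plan says.** SAP 4.3.1 lists two exploratory PSA endpoints. The first is "Maximum reduction in PSA (% change) from baseline". The second is best PSA response, taken as the greatest reduction "among all the changes from every post-baseline PSA value to its prior largest PSA value".

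SAP 9.2 carries both into waterfall plots, one from baseline and one "for best reduction in PSA (%) from any timepoint".

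SAP 9.1, under the secondary efficacy endpoints, also plans a waterfall of best PSA response. There the reference is baseline: "the maximum percent change in PSA levels since baseline will be depicted on the response axis".

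Protocol 9.5.5 and the synopsis include "Distribution of the best PSA response" among the summaries for the secondary efficacy objective, without giving a reference value. SAP section 13 declares two changes from the protocol, the treatment-emergent period and the definition of baseline. It mentions neither the prior-peak rule nor the listing of this endpoint as exploratory.

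The PSA responder endpoint is separate. SAP 4.2.2 defines it as "A reduction in PSA level from baseline by 50% or more", and the sample-size section uses the same reference.

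**The concern.** There are two problems.

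- **One name, two quantities.** A programmer cannot satisfy 4.3.1 and 9.1 with one derived variable, and a reader of a figure titled best PSA response cannot tell which reference was used.
- **The prior-peak rule rewards any dip after a rise.** It can show a reduction in a patient whose PSA was above baseline at every visit. This population is prone to that pattern: Protocol 4.1 requires rising PSA in Segment 2 and progressive disease by PSA or imaging in Segment 1 and the Expansion Phase. The Expansion cohorts have no concurrent control against which such dips could be judged.

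At stake is how a planned activity display is read, and whether a summary that the protocol places under a secondary objective is reported as a reader of the protocol would expect.

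**Working it through.** **Inputs.** The two definitions come from SAP 4.3.1 and 9.1. Baseline comes from SAP 7.2: "a baseline value will be defined as the most recent value on or before the first dose of exicorilant". PSA is measured on Day 1 of each cycle (Protocol 3.1). The documents give no within-patient PSA variability and no expected drift, so those are assumptions.

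**Formulas.** Let y0 be baseline and y1, y2, ... the later values.

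- Prior-peak rule (4.3.1): minimum over t of y_t / max(y0, ..., y_(t-1)) - 1
- Baseline rule (9.1): minimum over t of y_t / y0 - 1

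**Worked series (invented values, baseline first).**

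| PSA series | Prior-peak rule | Baseline rule |
|---|---|---|
| 20, 60, 30 | 30/60 - 1 = -50% | 30/20 - 1 = +50% |
| 20, 40, 20 | 20/40 - 1 = -50% | 20/20 - 1 = 0% |
| 10, 40, 15 | 15/40 - 1 = -62.5% | 15/10 - 1 = +50% |
| 10, 8, 4 | 4/10 - 1 = -60% | 4/10 - 1 = -60% |
| 10, 12, 14, 16 | 16/14 - 1 = +14% | 12/10 - 1 = +20% |

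The rules agree when PSA never exceeds baseline, and neither shows a fall when PSA only rises. They part when PSA peaks above baseline and then drops. A prior-peak fall of 50% or more in a patient never below baseline needs y_t >= y0 and y_t <= 0.5 x peak, so the peak must be at least twice baseline.

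The wording also leaves open whether baseline counts as a prior value. If only post-baseline values count, 10, 8, 4 gives 4/8 - 1 = -50% instead of -60%. The first three series give the same result either way.

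**How often, with no drug effect.** I simulated log-normal noise around a flat PSA, or around one rising 0.10 log units per cycle (exp(0.10) = 1.105, about 10.5%). Each patient had a baseline and six post-baseline values.

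| Trend | CV | Negative by prior-peak rule, never below baseline | Fall of 50% or more by prior-peak rule, never below baseline | Fall of 50% or more, all patients: prior-peak / baseline rule |
|---|---|---|---|---|
| Flat | 15% | 14% | <0.1% | 0.9% / 0.3% |
| Flat | 20% | 14% | 0.3% | 10% / 3% |
| Flat | 30% | 14% | 3.2% | 46% / 18% |
| Rising | 15% | 56% | <0.1% | 0.1% / <0.1% |
| Rising | 20% | 50% | 0.5% | 1.7% / 0.3% |
| Rising | 30% | 40% | 5.5% | 21% / 5% |

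The flat-PSA figure of 14% needs no CV. With seven exchangeable values, baseline is the smallest with probability 1/7. The prior-peak rule then gives a fall unless all seven values are in rising order (probability 1/5040). So 1/7 - 1/5040 = 14.3%.

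With three post-baseline values the first column becomes 1/4 - 1/24 = 20.8% for flat PSA and 32 to 38% for rising PSA. The second column is then at most 1.6%.

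**The plan's decision figures.** The exact binomial calculation with 20 patients reproduces the stated power and thresholds:

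- Abi-Resistant Cohort, 8 or more responders (40%): P(X >= 8 | 0.235) = 0.075 and P(X >= 8 | 0.47) = 0.802.
- ARant-Resistant Cohort, 4 or more responders (20%): P(X >= 4 | 0.08) = 0.071 and P(X >= 4 | 0.26) = 0.804.

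These use the baseline-referenced responder rate, so the best PSA response definition does not enter them.

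**The case against.** The strongest defence is that the prior-peak measure is a deliberate supplement. It sits beside maximum reduction from baseline in 4.3.1, the two waterfalls in 9.2 carry different labels, and the SAP classes both endpoints as exploratory. A reader who sees both figures can compare them. No cut-off is attached to the prior-peak value, and no decision uses it. All of that stands, and it limits the point to labelling and interpretation.

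A reader might go further and infer that a patient never below baseline can be counted as a PSA responder, or that the Expansion decision is biased. The documents do not support this. Section 4.3.1 describes a continuous percent change and classifies nobody. The responder endpoint is referenced to baseline in SAP 4.2.2, section 5 and 9.1.

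The simulation also needs careful reading. The last column of the second table counts every patient, including many who did fall below baseline, so it overstates the specific problem. The column for falls of 50% or more in patients never below baseline is the relevant one, and its values are small.

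The defence does not answer the conflict with 9.1, where the same name has a baseline reference. Nor does it answer the silence in section 13 on an endpoint that the protocol lists under a secondary objective.

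**Conclusion.** The point holds as a definitional conflict with a misleading consequence. SAP 4.3.1 and 9.1 give best PSA response different reference values, and the 4.3.1 rule can show a reduction in a patient whose PSA never fell below baseline. That much follows from the wording and simple arithmetic.

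Its frequency depends on assumptions. With six post-baseline values, no drug effect and CVs of 15 to 30%, about 14% of patients with flat PSA and 40 to 56% with PSA rising 0.10 log units per cycle would show a negative value while never below baseline. Falls of 50% or more in such patients are at most about 5.5%, and below 1% at a CV of 20% or less.

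The effect is confined to this exploratory measure and its waterfall. The baseline-referenced maximum reduction is already planned, and the 50% responder endpoint, the 40% and 20% thresholds and the power are untouched.

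**What to change.** 1. Define best PSA response once, as the maximum percent decline from baseline, or the smallest rise if there is no decline. This matches SAP 9.1. Merge it with the first bullet of 4.3.1, which is then the same quantity.
2. Either delete the prior-peak measure and the any-timepoint waterfall in 9.2, or rename both as maximum decline from prior peak, descriptive only and not evidence of response. If the measure is kept, state whether baseline counts as a prior value.
3. Record the choice in SAP section 13, together with whether the endpoint is secondary, as the protocol lists it, or exploratory.

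The cost is a few lines of SAP text and, if the measure is deleted, one fewer figure. No new data are needed and the sample size does not change.
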